Table A provides an overview of the protocol visits and procedures. Refer to [Section 6](#) and [Section 7](#) for detailed information on each procedure and assessment required for compliance with the protocol. The investigator *may* conduct unplanned visits, including safety-related laboratory tests on Day -1 with results reported by *local* laboratory prior to dosing on Day 1 *in addition* to those listed below, to conduct procedures to protect the well-being of the subject.

TABLE A. All procedures occurring at same nominal time as meals will occur prior to meal *except* dosing at 0H on Day 1 which is to occur with meal

Visit Identifier/Day [for list of abbreviations refer to Appendix 1]	Screen ≤-28	-1	1										2		3 ^a	4	5	6	Follow-Up	
			0	1	2	3	4	5	8	10	16	24	36	48	72	96	120	7	30±2	
Hours Post Dose		--	0	1	2	3	4	5	8	10	16	24	36	48	72	96	120	144	--	
Informed consent & demography	x																			
Outpatient visit	x														x ^a	x ^a	x ^a	x ^a		
Inpatient stay at Clinical Research Unit		x	→	→	→	→	→	→	→	→	→	→	→	x	x	x	x	x		
Eligibility assessment with CPC at Screen, only (Appendix 2)	x	x																		
(Update) Medical history	x	x																	x	
Physical exam (height & body weight at Screen, only) ^b	x	x												x					x	
Breath alcohol test	x	x																		
(Update) alcohol/tobacco & contraception use	x	x													x ^c	x ^c	x ^c	x ^c	x ^d	
(Update) prior/concomitant treatments	x	x													x ^c	x ^c	x ^c	x ^c	x	
Single, supine 12-lead ECG	x		x				x							x					x	
Single, seated vital sign assessment (BP and pulse rate)	x		x				x							x					x	
Serious and non-serious adverse event monitoring	x	x	→	→	→	→	→	→	→	→	→	→	→	→	→	→	→	x	x	
Standard meals ^e		x	x				x				x			x	x	x	x	x		
Investigational product administration			x ^f																	
Blood Samples for –																				
Clinical laboratory tests - after ≥4-hr fast (see Section 7.2.1)	x		x											x					x	
Serum FSH in females amenorrheic ≥12-months only	x																			
Pregnancy (females only)	x		x																x	
CCI																				
PF-05221304 PK			x	x	x	x	x	x	x	x	x	x	x	x	x	x	x	x		
PF-05221304 unbound fraction for protein binding							x													
Urine Samples for –																				
Urine drug test	x																			
Urinalysis (and microscopy, if needed)	x		x											x					x	
On-site pregnancy test (WOCBP, only)			x																x	

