In addition, subjects without hepatic impairment (Cohort 1) presenting with any of the following will ***not*** be included in the study:

1. Evidence of chronic liver disease including history of hepatitis, hepatitis B, or hepatitis C ***or*** evidence of ***any*** of the following, as assessed by sponsor-identified central laboratory, with a single repeat, permitted to assess eligibility, if needed –
 - Hepatitis B virus, defined by presence of hepatitis B surface antigen (HBsAg);
 - ***NOTE***: while ***not*** part of the tests assessed in this study, subjects with a previously positive HBsAb result due to vaccination, are deemed eligible;
 - Hepatitis C virus (HCV), defined by presence of hepatitis C antibody (HCVAb) and HCV RNA (when reflexed based on a positive result for HCVAb);
2. History of regular alcohol consumption exceeding 14 drinks/week for female subjects or 21 drinks/week for male subjects (1 drink = 5 ounces [150 mL] of wine or 12 ounces [360 mL] of beer or 1.5 ounces [45 mL] of hard liquor) within 6 months of before Screening;
3. Evidence or history of clinically significant hematological, renal, endocrine, pulmonary, gastrointestinal, cardiovascular, hepatic, psychiatric, neurologic, or allergic disease (including drug allergies, but excluding untreated, asymptomatic, seasonal allergies at the time of dosing);
4. Screening ***supine*** 12-lead ECG demonstrating QTcF interval >450 msec ***or*** a QRS interval >120 msec. If QTcF exceeds 450 msec, ***or*** QRS exceeds 120 msec, the ECG should be repeated 2 more times and the average of the ***three*** QTcF or QRS values should be used to determine the subject's eligibility;
5. Screening ***seated*** systolic blood pressure (SBP) ≥140 mm Hg ***or*** diastolic blood pressure (DBP) ≥90 mm Hg, following ≥5 minutes of seated rest. If SBP is ≥140 mm Hg ***or*** DBP ≥90 mm Hg, the BP assessment should be repeated 2 more times and the average of the ***three*** BP values should be used to determine the subject's eligibility;
6. Use of ***chronic*** prescription medications within **7 days or 5 half-lives** (whichever is longer) prior to Day 1 –
 - ***NOTE***: use of selected, limited prescription and non-prescription medications is permitted – refer to [Section 5.8.1](#) for details;

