9. At Screening, persistent severe, uncontrolled hypertension; for example: *seated* systolic blood pressure (SBP) ≥ 180 mm Hg and/or diastolic blood pressure (DBP) ≥ 105 mm Hg after ≥ 5 -minute of seated rest, with a single repeat permitted to assess eligibility, if needed, at each of these 2 visits:
 - For subjects with SBP ≥ 160 mm Hg **or** DBP ≥ 100 mm Hg, the period between Screening and Day -1 must be used to refine the doses of the agents used for management of blood pressure (refer to [Section 5.8.2](#)) with the aim to have stable BP on Day 1 [refer to [Section 4.3](#)];
10. Subjects with ALT **or** AST $>5x$ ULN on clinical laboratory tests at Screening, as assessed by the sponsor-identified central laboratory, with a single repeat permitted to assess eligibility, if needed.

4.3. Criteria for Dosing on Day 1

Subjects will progress to dosing on Day 1 provided they have satisfied **all** the following criteria –

- Eligibility criteria outlined in [Section 4.1](#) and [Section 4.2](#);
- Breath Alcohol test on Day -1 is negative;
- In females of childbearing potential, *urine* pregnancy test on Day 1 prior to dosing as reported by *on-site* pregnancy test using supplies offered by sponsor-identified central laboratory, is negative for pregnancy – refer to [Section 7.2.1.1](#);
- Safety-related laboratory tests collected and analyzed by sites' *local* laboratory on Day -1, *if performed* at investigator discretion, upon review on Day 1 must reflect subject to be in stable medical condition;
- **Cohorts 2, and 3, only:** patients with elevated BP at Screening must have measurement on Day 1 of SBP ≤ 159 mm Hg **and** DBP ≤ 99 mm Hg with repeat permitted, if needed, to confirm stable BP;
- **Cohort 4, only:** patients with elevated BP at Screening must have measurement on Day 1 of SBP ≤ 159 mm Hg **and** DBP ≤ 105 mm Hg with repeat permitted, if needed, to confirm stable BP.

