7.2.3. Blood Pressure and Pulse Rate

Blood pressure and pulse rate will be measured as defined in the Schedule of Activities [Table A](#). Additional collection times, or changes to collection times of blood pressure and pulse rate will be permitted, as necessary, to ensure appropriate collection of safety data.

- **Single, seated** blood pressure/pulse rate will be measured with the subject's arm supported at the level of the heart, and recorded to the nearest mm Hg, following a rest of **≥5-minutes**; the assessment at Visit 5 (Day 1) will serve as each subject's baseline;
- Same arm (preferably the dominant arm) will be used for blood pressure/pulse rate assessment throughout the study;
- Blood pressure/pulse rate assessment should not be taken from the arm with an intravenous catheter, if placed;
- Subjects should be instructed not to speak during blood pressure/pulse rate measurements.

The same properly sized and calibrated blood pressure cuff will be used to measure blood pressure each time. The use of an automated device for measuring BP and pulse rate is acceptable, although, when done manually, pulse rate will be measured in the brachial/radial artery for **≥30 seconds**.

Refer to [Section 6.1](#) for proposed chronology of procedures for nominal time points when vital sign assessments coincide with other procedures.

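### The numeric Day 1 blood-pressure limits in Section 4.3 bind only Cohort 2–4 subjects already elevated at Screening, so a new rise by Day 1 meets no numeric 4.3 limit

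*Protocol*

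**What the plan says.** Protocol Section 4.3 lists what must be satisfied before dosing. Two of its bullets concern blood pressure, one for Cohorts 2 and 3 and one for Cohort 4, and both open with the same condition: "patients with elevated BP at Screening must have measurement on Day 1 of SBP" ≤159 mm Hg. The accompanying DBP limit is ≤99 mm Hg in Cohorts 2 and 3 and ≤105 mm Hg in Cohort 4. A repeat is allowed in both. No other bullet in 4.3 sets a blood-pressure limit.

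Section 4.2.2, exclusion 9, deals with severe hypertension in Cohorts 2–4. It begins "At Screening, persistent severe, uncontrolled hypertension; for example" and gives SBP ≥180 and/or DBP ≥105 as the example, "with a single repeat permitted to assess eligibility, if needed, at each of these 2 visits". No second visit is named. Its sub-bullet takes subjects with SBP ≥160 or DBP ≥100 and says that "the period between Screening and Day -1 must be used to refine the doses of the agents used for management of blood pressure", "with the aim to have stable BP on Day 1", with a cross-reference to Section 4.3.

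Section 7.2.3 makes the Day 1 reading the baseline for each subject ("the assessment at Visit 5 (Day 1) will serve as each"), Table A schedules it at 0H for everyone, and Section 6.1 places vital signs before dosing.

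**The concern.** The Day 1 reading decides whether a subject who was elevated at Screening can be dosed, but 4.3 attaches no numeric consequence to the same reading in a subject who was not. The limit is there to confirm that pressure is stable. Yet the subject whose pressure has moved most since Screening can be the one who faces no limit.

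A new rise is foreseeable. Under Section 6.2 Screening may be up to 28 days before dosing. Section 4.1.2 lets some subjects on fluctuating background medication enter case by case. The required refinement of antihypertensive doses applies only to those at or above 160/100 at Screening.

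What is at stake is safety on the dosing day and consistency between sites in a multisite study. Section 1.4 expects no clinical benefit for participants.

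**Working it through.** No figure in the plan needs reproducing. The check sets the rules side by side and finds the Day 1 readings for which the dosing decision depends on Screening status. Section 7.2.3 records pressure to the nearest mm Hg, so whole numbers suffice.

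**1. Meaning of elevated.** The exclusion 9 sub-bullet identifies SBP ≥160 or DBP ≥100 and points to 4.3. Not being in that group means SBP ≤159 and DBP ≤99, which is exactly the 4.3 limit for Cohorts 2 and 3. I therefore take 160/100 as the implied cut-off.

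**2. Two subjects with the same Day 1 reading.**

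| | Subject A | Subject B |
|---|---|---|
| Screening | 136/84 | 162/95 |
| Elevated at Screening (160/100)? | No | Yes |
| Below the exclusion 9 example (180/105) at Screening? | Yes | Yes |
| Day 1 | 170/95 | 170/95 |
| Rise in SBP | 170 − 136 = 34 | 170 − 162 = 8 |
| Numeric limit in 4.3 | None | SBP ≤159 with DBP ≤99 (Cohorts 2–3) or ≤105 (Cohort 4) |
| Result under 4.3 | Left to investigator discretion | Barred unless the repeat is within limits |

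170/95 is also below 180/105, so the contrast is the same whether or not the exclusion 9 example is applied again on Day 1.

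**3. Range of Day 1 readings affected.** The text allows two readings of exclusion 9. Each band below varies one component and holds the other within limits.

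| | Exclusion 9 not applied on Day 1 | Example values also applied on Day 1 |
|---|---|---|
| Cohorts 2–3, SBP | ≥160, no ceiling | 160–179 |
| Cohorts 2–3, DBP | ≥100, no ceiling | 100–104 |
| Cohort 4, SBP | ≥160, no ceiling | 160–179 |
| Cohort 4, DBP | ≥106, no ceiling | none |

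The last cell is empty because the example would bar DBP ≥105 in everyone, and an elevated Cohort 4 subject passes at anything lower. If the unnamed second visit were Day -1, the Day 1 reading would still have no ceiling, so the first column would apply.

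**4. Smallest rise that enters the gap.** SBP: 160 − 159 = 1 mm Hg. DBP in Cohorts 2–3: 100 − 99 = 1 mm Hg. DBP in Cohort 4, first column only: 106 − 99 = 7 mm Hg.

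**5. Number at risk.** Planned Cohort 2–4 subjects: 3 × 6 = 18, or 6 + 6 + 4 = 16 if Cohort 4 stops at 4 (Table 1, footnote b). The documents give no blood-pressure distribution, so the number falling in the gap cannot be estimated.

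**6. After the fix.** If each 4.3 limit applied to every subject in its cohorts, no Day 1 reading would remain for which the decision depends on Screening status.

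**The case against.** *The condition has a purpose.* Exclusion 9 admits subjects with Screening SBP of 160–179 on the footing that their treatment is refined, and 4.3 checks that the refinement worked. Leaving an isolated high reading in anyone else to clinical judgment is an ordinary Phase 1 choice. Nothing visible in the documents shows that a predose SBP of 160–179 makes a single 25 mg dose riskier. This explains why elevated subjects are checked. It does not explain why a newly hypertensive subject should be exempt, but it does keep the point small.

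*Discretion already covers it.* Section 4 asks that all relevant conditions be weighed, 6.5 allows withdrawal for safety, 7.2.3 allows extra readings, and Section 1.4 provides at least 48 hours of inpatient monitoring. These safeguards are real. They give sites no common limit, however, and the explicit exclusion based on investigator judgment (4.2.1, criterion 7) applies to Cohort 1 only.

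*Exclusion 9 closes the gap.* It does not do so clearly: it is anchored at Screening, its values are an example, and its second visit is unnamed. Applied on Day 1, it would still leave SBP 160–179 open, as well as DBP 100–104 in Cohorts 2–3.

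Some stronger readings are tempting but not supported:

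- A reader might infer that elevated has no usable meaning, or might mean 140/90. The exclusion 9 sub-bullet implies 160/100. The other cut-off ("systolic blood pressure (SBP) ≥140 mm Hg", with DBP ≥90) is a Cohort 1 criterion in 4.2.1, and Cohort 1 has no blood-pressure bullet in 4.3.
- A reader might infer that subject A will be dosed and subject B cannot be. The investigator may withhold dosing from A, and B may pass on the repeat.
- A reader might infer that the reference to two visits is stray text to delete. The documents do not show that; it may be an intended second check.

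**Conclusion.** The point holds for Cohorts 2–4. Section 4.3 sets no numeric Day 1 limit for a subject below 160/100 at Screening, so the same Day 1 reading can bar one subject and leave another to discretion. The affected readings start at SBP 160 in all three cohorts and at DBP 100 in Cohorts 2–3. Whether they have a ceiling depends on how exclusion 9 is read.

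The conclusion assumes that the exclusion 9 sub-bullet supplies the meaning of elevated, which the text implies but does not state. The choice of 160/100 does not drive the example, because 136/84 is below either cut-off in the protocol and 162/95 is above both.

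This is a small gain in dosing-day safety and site consistency, worth considering because it is cheap. The number of subjects affected is unknown and probably small. The PK analysis and the sample size are unaffected.

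**What to change.** In both blood-pressure bullets of Section 4.3, replace the words restricting the limit to subjects elevated at Screening with *every subject*. Keep the sponsor's own limits (≤159/≤99 in Cohorts 2–3, ≤159/≤105 in Cohort 4) and the permitted repeat.

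In exclusion 9, keep the reference to two visits and have the sponsor name the second. If it is Day 1, its DBP ≥105 example must be reconciled with the Cohort 4 limit: a DBP of exactly 105 passes 4.3 but meets the exclusion example.

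No new measurement is needed, because the 0H reading is already scheduled for everyone and taken before dosing. The cost is that an occasional subject, already admitted on Day -1, is deferred. That subject must be re-admitted within the original 28-day Screening window or may be lost. Section 6.2 allows re-screening when logistics push past 28 days or, in Cohorts 2–4, after a mild illness has resolved, and a failed Day 1 reading fits neither clearly. The loss would matter most in Cohort 4, where the plan already foresees stopping at 4 subjects.

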4.4. Lifestyle Requirements

After confirmation of eligibility and starting on Day -1, the subjects will be instructed to maintain the guidelines described below for the duration of participation in the study.

4.4.1. Meals and Dietary Restrictions

While inpatient, the meals consumed are expected to follow the restrictions outlined below with subjects encouraged to complete each meal.

- Subjects must abstain from all food and drink (except water) for ≥ 4 -hours prior to all fasting clinical laboratory evaluations;
- Water may be consumed as desired (ad libitum);
- Investigational product must be administered with the morning meal;
- **While inpatient**, meals including on non-dosing days – will be standardized as follows –
 - Standard morning meal, lunch, afternoon snack, and evening meal (and an optional evening snack) will be provided at a similar clock time to the clock time when these meals are offered on Day 1 (ie, 0H, 4H, 7H, 10H, and 14H);
 - The total daily nutritional composition should be **approximately 55% carbohydrate, 30% fat and 15% protein**;
 - The daily caloric intake per subject should not exceed approximately 3200 kcal;
 - The morning meal (matching 0H), afternoon snack, **and** optional evening snack is **each** envisioned to constitute 300-400 calories **and** a macronutrient composition of approximately 55% carbohydrates, 30% fat and 15% protein;
 - Lunch and evening meal **each** is envisioned to constitute less than 1000 calories;
 - The nutritional macronutrient composition consumed by each subject should be maintained, as much as practically possible;
 - If subjects cannot complete the meals, the portion consumed in 25% increments will be documented and potential impact on results assessed by the Sponsor study team on a case-by-case basis;
 - **On Day 1**, the morning meal will be provided at approximately 30 minutes prior to dosing at 0H (or similar clock time on non-dosing days) and is expected to be completed approximately 10 minutes prior to dosing;
- **During the outpatient visits** on Days 4 through 7, inclusive, as applicable, a morning meal will be consumed at the site following completion of the other procedures at this nominal time point [with the meal either provided by the site or the subject provided a voucher (or similar) by the site to purchase the meal before arriving to the site for each visit].

4.4.2. Alcohol, Caffeine, and Tobacco

- Subjects will abstain from alcohol for ≥ 24 hours prior to the single dose of investigational product (IP) on Day 1 (*plus* have a negative breath alcohol test on Day -1) and continue abstaining from alcohol until the on-site Follow-up visit (Day 7);
 - Subjects will undergo a breath alcohol test at time points indicated in the Schedule of Activities (Table A);
- Consumption of caffeinated drinks and nicotine-containing products is permitted during participation in the study; however, there may be a need for brief interruption while at the site, depending on local site policy.

4.4.3. Activity

- Subjects will **not** be permitted to engage in physically strenuous exercise (for example: heavy lifting, weight training, calisthenics, and aerobics) within **48-hours** before each blood sample collection for clinical laboratory tests while participating in the study; physical activity at an individual subject's normal pace is permitted.

4.4.4. Contraception

CCI [REDACTED]

Female subjects who, *in the opinion of the investigator* are sexually active *and* at risk for pregnancy must agree to use, with their partner(s), highly effective contraception throughout the study and continue use for **at least 28 days** after receiving the single dose of the investigational product. The investigator or his or her designee, in consultation with the subject, will confirm that the subject has selected the appropriate method of contraception for the individual subject from the list of permitted contraception methods below and instruct the subject in their consistent and correct use. At time points indicated in the Schedule of Activities (Table A), the investigator or designee will inform the female subject of the need to use the highly effective method of contraception consistently and correctly and document such conversation, and the subject's affirmation, in the subject's chart.

Highly effective methods of contraception are those that, alone or in combination, result in a failure rate of less than 1% per year when used consistently and correctly (ie, perfect use). **One** of the below options must be used to satisfy the requirement for highly effective contraception in female subjects participating in this study:

1. Established use of hormonal methods of contraception associated with inhibition of ovulation (eg, inserted, injected, implanted; *and* including oral, as well as transdermal methods unless prohibited by local regulations or ethics committee decision), with *either*:
 - a. Male *or* female condom;
 - b. Male sterilization.
2. Correctly placed copper-containing intrauterine device (IUD) or intrauterine system combined with *either*:
 - a. Male *or* female condom;
 - b. Male sterilization.
3. Male sterilization with absence of sperm in the post-vasectomy ejaculate in the female subjects' partner combined with *either*:
 - a. Male *or* female condom;
 - b. Bilateral tubal ligation/bilateral salpingectomy or bilateral tubal occlusive procedures.
4. Bilateral tubal ligation/bilateral salpingectomy or bilateral tubal occlusive procedure (provided that occlusion has been confirmed in accordance with the device's label) **combined with one** of the following:
 - a. IUD *or* intrauterine system;
 - b. Male *or* female condom;
 - c. Male sterilization.

All sexually active male subjects must agree to prevent potential transfer to and exposure of female partner(s) to drug through ejaculate by using a condom consistently and correctly, beginning with the dose of investigational product (Day 1) and continuing for **at least 28 days** after the dose of investigational product.

In female subjects, pregnancy testing will be performed at time points indicated in the Schedule of Activities (Table A). The specific contraceptive method(s) in the females of childbearing potential will be documented, and ***at every visit*** their consistent and correct use will be ascertained and documented in the subject's source document. For additional details, refer to Section 7.2.1.1.

In addition, the investigator or designee will instruct ***all subjects of childbearing potential*** to call immediately if the selected contraception method is discontinued or if pregnancy is known or suspected in the female subject *or* male subjects' female partner.

NOTE: Sexual abstinence, defined as completely and persistently refraining from all heterosexual intercourse (including during the entire period of risk associated with this study) *may* obviate the need for contraception **ONLY** if this is the preferred and usual lifestyle of the subject.

4.5. Sponsor's Qualified Medical Personnel

The contact information for the sponsor's appropriately qualified medical personnel for the study is documented in the study contact list located in the supporting study documentation.

To facilitate access to appropriately qualified medical personnel on study-related medical questions or problems, subjects are provided with a contact card. The contact card contains, at a minimum, protocol and investigational product identifiers, subject study numbers, contact information for the investigator site, and contact details for a contact center in the event that the investigator site staff cannot be reached to provide advice on a medical question or problem originating from another healthcare professional not involved in the subject's participation in the study. The contact number can also be used by investigator staff if they are seeking advice on medical questions or problems; however, it should be used only in the event that the established communication pathways between the investigator site and the study team are not available. It is therefore intended to augment, but not replace, the established communication pathways between the investigator site and the study team for advice on medical questions or problems that may arise during the study. ***For sites other than a Pfizer clinical research unit (CRU)***, the contact number is not intended for use by the subject directly, and if a subject calls that number, he or she will be directed back to the investigator site.

